12.4.3 Criteria for Causal Relationship to Investigational Product

A medically qualified investigator is obligated to assess the relationship between IP and each occurrence of each (S)AE. This investigator will use medical judgment as well as the reference safety information to determine the relationship. The causality assessment is one of the criteria used when determining regulatory reporting requirements.

The investigator is requested to provide an explanation for the causality assessment for each (S)AE and must document in the medical notes that he/she has reviewed the (S)AE and has provided an assessment of causality.

Following a review of the relevant data, the causal relationship between the IP and each (S)AE will be assessed by answering “yes” or “no” to the question “Do you consider that there is a reasonable possibility that the event may have been caused by the IP?”

When making an assessment of causality, the following factors are to be considered when deciding if there is evidence and/or arguments to suggest there is a “reasonable possibility” that an (S)AE may have been caused by the IP (rather than a relationship cannot be ruled out) or if there is evidence to reasonably deny a causal relationship:

- Has the subject been administered IP?
- Plausibility (i.e., could the event have been caused by the suspect drug? Consider biologic and/or pharmacologic mechanism, half-life, literature evidence, drug class, preclinical and study data, etc.)
- Dechallenge/dose reduction/rechallenge:
 - Dechallenge: Did the (S)AE resolve or improve after only stopping the dose of the suspect drug without any treatment?
 - Dose reduction: Did the (S)AE resolve or improve after reducing the dose of the suspect drug?
 - Rechallenge: Did the (S)AE reoccur if the suspected drug was reintroduced after having been stopped?

- Laboratory or other test results: a specific laboratory investigation supports the assessment of the relationship between the (S)AE and the IP (e.g., based on values pretreatment, during and posttreatment)
- Available alternative explanations independent of IP exposure; such as other concomitant drugs, past medical history, concurrent or underlying disease, risk factors including medical and family history, season, location, etc., and strength of the alternative explanation
- Finally, judging which are more likely based on all the above contents, factors of reasonable possibility or confounding factors, comprehensive judgment of plausible temporal relationship between exposure to the IP and (S)AE onset and/or resolution will be provided. Did the (S)AE occur in a reasonable temporal relationship to the administration of the IP?

There may be situations in which an SAE has occurred, and the investigator has minimal information to include in the initial report to the sponsor. However, it is very important that the investigator always assesses causality for every event before the initial transmission of the SAE data to the sponsor. With limited or insufficient information about the event to make an informed medical judgment and in absence of any indication or evidence to establish a causal relationship, a causality assessment of “no” is to be considered. In such instance, the investigator is expected to obtain additional information regarding the event as soon as possible and to re-evaluate the causality upon receipt of additional information. The medically qualified investigator may revise his/her assessment of causality in light of new information regarding the SAE and shall send an SAE follow-up report and update the eCRF with the new information and updated causality assessment.

12.4.4 Criteria for Defining the Severity of an Adverse Event

AEs, including abnormal clinical laboratory values, will be graded using the NCI-CTCAE guidelines Version 4.03. The items that are not stipulated in the NCI-CTCAE Version 4.03 will be assessed according to the criteria below and entered into the eCRF:

Table 12 Grading Scale Defining the Severity of an Adverse Event

Grade	Assessment Standard
1 - Mild	Asymptomatic or mild symptoms, clinical or diagnostic observations only; intervention not indicated
2 - Moderate	Minimal local or noninvasive intervention indicated; limiting age-appropriate instrumental ADL†
3 - Severe	Medically significant but not immediately life-threatening, hospitalization or prolonged hospitalization indicated; disabling; limiting selfcare ADL‡
4 - Life-threatening	Life-threatening consequences, urgent intervention indicated
5 - Death	Death related to AE

ADL: activities of daily living; AE: adverse event

†Instrumental ADL refer to preparing meals, shopping for groceries or clothes, using the telephone, managing money, etc.

‡Selfcare ADL refer to bathing, dressing and undressing, feeding self, using the toilet, taking medications and not bedridden.

12.4.5 Reporting Procedures for Serious Adverse Events

The investigator must complete and submit an SAE worksheet containing all information that is required by local and/or regional regulations to the sponsor by fax or email immediately (within 24 hours of awareness).

The SAE worksheet must be signed by a medically qualified investigator (as identified on delegation of authority log). Signature confirms accuracy and completeness of the SAE data as well as the investigator causality assessment including the explanation for the causality assessment.

For contact details, see [Contact Details of Sponsor's Key Personnel]. Fax or email the SAE/special situations worksheet to:

Astellas Pharma Global Development Inc.
Pharmacovigilance
North America fax number: [[contact]]
North America alternate fax number: [[contact]]
International [contact]
Email: [contact]

For investigational sites located in Japan:

In the case of a SAE, the investigator or subinvestigator must report to the head of the study site and must contact the sponsor by fax or email immediately (within 24 hours of awareness).

The investigator should complete and submit JUTOKUNA YUUGAIJISHOU HOUKOKUSHO containing all information that is required by the appropriate regulatory authorities to the sponsor (by fax or email immediately [within 24 hours of awareness]) and to the head of the hospital.

JUTOKUNA YUUGAIJISHOU HOUKOKUSHO the SAE/special situations worksheet to:

Astellas Pharma Inc. – Japan
Pharmacovigilance
[contact]
Email: [contact]

If there are any questions, or if clarification is needed regarding the SAE, please contact the sponsor's medical monitor/study physician or their designee [Contact Details of Sponsor's Key Personnel].

Follow-up information for the event should be sent promptly (as soon as available but no longer than within 7 days of the initial notification).

Full details of the SAE should be recorded on the medical records, SAE/special situations worksheet and on the eCRF.

The following minimum information is **required**:

- International study number/study number
- Subject number, sex and age
- Date of report
- Description of the SAE (event and seriousness criteria)
- Causal relationship to the IP (including reason)
- Drug provided (if any)

The sponsor or sponsor's designee will medically evaluate the SAE and determine if the report meets the requirements for expedited reporting based on seriousness, causality, and expectedness of the events (e.g., suspected unexpected serious adverse reaction [SUSAR] reporting) according to current local/regional regulatory requirements. The sponsor or sponsor's designee will submit expedited safety reports to competent authorities and concerned ethics committee per current local regulations and will inform the investigators of such regulatory reports as required. Investigators must submit safety reports as required by their IRB/IEC within timelines set by regional regulations (e.g., EMA, FDA) where required. Documentation of the submission to and receipt by the IRB/ IEC of expedited safety reports should be retained by the study site. In the US, FDA expedited IND reporting guidelines will be followed.

The sponsor will notify all investigators responsible for ongoing clinical studies with the test product of all SUSARs, which require submission per local requirements IRB/IEC.

Investigators should provide written documentation of IRB/IEC notification for each report to the sponsor.

The investigator may contact the sponsor's medical monitor/study physician for any other problem related to the rights, safety or well-being of the subject.

12.4.6 Reporting Procedures for Special Situations

12.4.6.1 Pregnancy

If a female subject becomes pregnant during the study dosing period or within 6 months from the discontinuation of dosing, the investigator is to report the information to the sponsor according to the timelines in [Section 12.4.5 Reporting Procedures for Serious Adverse Events] using the pregnancy reporting form as a special situation and in the eCRF.

The investigator will attempt to collect pregnancy information on any female partner of a male subject who becomes pregnant during the study dosing period or within 6 months from the discontinuation of dosing and report the information to the sponsor according to the timelines in [Section 12.4.5 Reporting Procedures for Serious Adverse Events] using the pregnancy reporting form as a special situation.

The expected date of delivery or expected date of the end of the pregnancy, last menstruation, estimated conception date, pregnancy result and neonatal data, etc., should be included in this information.

While pregnancy itself is not considered to be an AE or SAE, any pregnancy complication or termination (including elective termination) of a pregnancy is to be reported for a female subject as an AE in the eCRF or SAE per [Section 12.4.5 Reporting Procedures for Serious Adverse Events]. For (S)AEs experienced by a female partner of a male subject, (S)AEs are to be reported via the SAE worksheet.

Additional information regarding the outcome of a pregnancy when also categorized as an SAE is mentioned below:

- “Spontaneous abortion” includes miscarriage, abortion and missed abortion.
- Death of a newborn or infant within 1 month after birth is to be reported as an SAE regardless of its relationship with the IP.
- If an infant dies more than 1 month after the birth, it is to be reported if a relationship between the death and intrauterine exposure to the IP is judged as “possible” by the investigator.
- Congenital anomaly (including anomaly in miscarried fetus).

Unless a congenital anomaly is identified prior to spontaneous abortion or miscarriage, the embryo or fetus should be assessed for congenital defects by visual examination or other means as appropriate. (S)AEs experienced by the newborn/infant should be reported via the pregnancy reporting form. Generally, follow-up will be no longer than 6 to 8 weeks following the estimated delivery date.

12.4.6.2 Medication Error, Overdose and “Off-label Use”

If a medication error (defined as an unintended failure in the treatment process that leads to, or has the potential to lead to, harm to the subject), overdose or “off-label use” (i.e., use outside of what is stated in the protocol) is suspected, refer to [Section 10.3 Major Protocol Deviations]. Any associated (S)AEs are to be reported in the eCRF. If the AE meets the definition of an SAE, the SAE is also to be reported as described in [Section 12.4.5 Reporting Procedures for Serious Adverse Events] together with the details of the medication error, overdose and/or “off-label use.”

In the event of suspected IP overdose, the subject should receive supportive care and monitoring. The medical monitor/expert should be contacted as applicable.

12.4.6.3 Misuse/Abuse

Definition of misuse: Situations where the IP is/are intentionally and inappropriately used not in accordance with the intended use as defined in the protocol.

Definition of abuse: Persistent or sporadic, intentional excessive use of medicinal products which is accompanied by harmful physical or psychological effects.

If misuse or abuse of the IP is suspected, the investigator must forward the special situations worksheet to the sponsor by fax or email immediately (within 24 hours of awareness). Any associated (S)AEs are to be reported in the eCRF. If the AE meets the definition of an SAE, the SAE is also to be reported as described in [Section 12.4.5 Reporting Procedures for Serious Adverse Events] together with details of the misuse or abuse of the IP.

12.4.6.4 Occupational Exposure

If occupational exposure (e.g., inadvertent exposure to the IP of study site personnel while preparing it for administration to the subject) to the IP occurs, the investigator must forward the special situations worksheet to the sponsor by fax or email immediately (within 24 hours of awareness). Any associated (S)AEs occurring to the individual associated with or resulting from the special situation are to be reported on the special situations worksheet.

12.4.6.5 (Suspicion of) Transmission of Infectious Agent

If transmission of an infectious agent associated with the IP is suspected, the investigator must forward the special situations worksheet to the sponsor by fax or email immediately (within 24 hours of awareness) and any associated (S)AEs are to be reported in the eCRF. If the AE meets the definition of an SAE, the SAE is also to be reported as described in [Section 12.4.5 Reporting Procedures for Serious Adverse Events] together with the details of the suspected transmission of infectious agent.

12.4.6.6 Suspected Drug-drug Interaction

If a drug-drug interaction associated with the IP is suspected, the investigator must forward the special situations worksheet to the sponsor by fax or email immediately (within 24 hours of awareness). Any associated (S)AEs are to be reported in the eCRF. If the AE meets the definition of an SAE, the SAE is also to be reported as described in [Section 12.4.5 Reporting Procedures for Serious Adverse Events] together with details of the suspected drug-drug interaction.

12.5 Liver Safety Monitoring and Assessment

The purpose of this appendix is to provide guidance for the monitoring of drug-induced liver injury during the course of the study. It should be noted that this section does not specify the End of Study analyses of liver enzymes. The end of study liver enzymes analyses will be described in the SAP. Any subject enrolled in a study with active drug therapy and who reveals an increase of serum aminotransferases (AT) to $> 3 \times \text{ULN}$ (to $> 5 \times \text{ULN}$ in subjects with liver metastases) or total bilirubin $> 2 \times \text{ULN}$ should undergo detailed testing for liver enzymes (including at least ALP, ALT, AST and TBL). Testing should be repeated within 72 hours of notification of the test results. For studies for which a central laboratory is used, alerts will be generated by the central laboratory regarding moderate and severe liver abnormality to inform the investigator and study team. Subjects should be asked if they have any symptoms suggestive of hepatobiliary dysfunction.

Definition of Liver Abnormalities

Confirmed abnormalities will be characterized as moderate and severe where ULN is as shown below.

Table 13 Moderate and Severe Liver Abnormalities

	ALT or AST		TBL
Moderate	$> 3 \times \text{ULN}$ (in subjects without liver metastases), $> 5 \times \text{ULN}$ (in subjects with liver metastases)	or	$> 2 \times \text{ULN}$
Severe	$> 3 \times \text{ULN}$	and†	$> 2 \times \text{ULN}$

ALT: alanine aminotransferase; AST: aspartate aminotransferase; TBL: total bilirubin; ULN: upper limit of normal

†Samples taken simultaneously or within maximum 24 hours.

In addition, the subject should be considered to have severe hepatic abnormalities for any of the following:

- ALT or AST $> 8 \times \text{ULN}$
- ALT or AST $> 5 \times \text{ULN}$ for more than 2 weeks (in the absence of liver metastases)
- ALT or AST $> 3 \times \text{ULN}$ and† TBL $> 2 \times \text{ULN}$ or international normalized ratio (INR) > 1.5 (If INR testing is applicable/evaluated)
- ALT or AST $> 3 \times \text{ULN}$ with the appearance of fatigue, nausea, vomiting, right upper quadrant pain or tenderness, fever, rash and/or eosinophilia ($> 5\%$)

† Samples taken simultaneously or within a maximum of 24 hours.

The investigator may determine that abnormal liver function results, other than those described above, may qualify as moderate or severe abnormalities and require additional monitoring and follow-up.

Follow-up Procedures

Confirmed moderate and severe abnormalities in hepatic functions should be thoroughly characterized by obtaining appropriate expert consultations, detailed pertinent history, physical examination and clinical laboratory tests. The study site personnel are to complete the liver

abnormality case report form (LA-CRF). Subjects with confirmed abnormal liver function testing should be followed as described below.

Confirmed moderately abnormal liver function tests should be repeated 2 to 3 times weekly then weekly or less if abnormalities stabilize or the investigational product has been discontinued and the subject is asymptomatic.

Severe hepatic liver function abnormalities as defined above, in the absence of another etiology may be considered an important medical event and may be reported as an SAE. The sponsor should be contacted and informed of all subjects for whom severe hepatic liver function abnormalities possibly attributable to investigational product are observed.

To further assess abnormal hepatic laboratory findings, the investigator is expected to:

- Obtain a more detailed history of symptoms and prior or concurrent diseases. Symptoms and new onset diseases are to be recorded as AEs in the eCRF. Illnesses and conditions such as hypotensive events and decompensated cardiac disease that may lead to secondary liver abnormalities should be noted. Nonalcoholic steatohepatitis is seen in obese hyperlipoproteinemic and/or diabetic subjects and may be associated with fluctuating AT levels. The investigator should ensure that the medical history form captures any illness that predates study enrollment that may be relevant in assessing hepatic function.
- Obtain a history of concomitant drug use (including nonprescription medication, complementary and alternative medications), alcohol use, recreational drug use and special diets. Medications, including dose, are to be entered in the eCRF. Information on alcohol, other substance use and diet should be entered on the LA-CRF or an appropriate document.
- Obtain a history of exposure to environmental chemical agents.
Based on the subject's history, other testing may be appropriate including:
 - Acute viral hepatitis (A, B, C, D, E or other infectious agents)
 - Ultrasound or other imaging to assess biliary tract disease
 - Other clinical laboratory tests including INR, direct bilirubin
- Consider gastroenterology or hepatology consultations.
- Submit results for any additional testing and possible etiology on the LA-CRF or an appropriate document.

Study Treatment Discontinuation

In the absence of an explanation for increased liver function tests, such as viral hepatitis, preexisting or acute liver disease, presence of liver metastases, or exposure to other agents associated with liver injury, the subject may be discontinued from study treatment. The investigator may determine that it is not in the subject's best interest to continue study treatment. Discontinuation of study treatment should be considered if:

- ALT or AST $> 8 \times$ ULN
- ALT or AST $> 5 \times$ ULN for more than 2 weeks (in subjects without liver metastases)
- ALT or AST $> 3 \times$ ULN and† TBL $> 2 \times$ ULN or INR > 1.5 (If INR testing is applicable/evaluated)

- ALT or AST $> 5 \times$ ULN and† (TBL $> 2 \times$ ULN in subjects with liver metastases)
- ALT or AST $> 3 \times$ ULN with the appearance of fatigue, nausea, vomiting, right upper quadrant pain or tenderness, fever, rash and/or eosinophilia ($> 5\%$)

† Samples taken simultaneously or within a maximum of 24 hours.

In addition, if close monitoring for a subject with moderate or severe hepatic laboratory tests is not possible, study treatment should be discontinued.

Hy's Law Definition:

1. Evidence that a drug can cause hepatocellular-type injury, generally shown by a higher rate than control of people with $3 \times$ AT elevations over the ULN ($2 \times$ elevations are too common in treated and untreated subjects to be discriminating).
2. Cases of increased bilirubin (to at least $2 \times$ ULN) in people with concomitant AT elevation to at least $3 \times$ ULN (but it is almost invariably higher) and no evidence of intra- or extra-hepatic bilirubin obstruction (elevated ALP) or Gilbert's syndrome [Temple, 2006].

FDA Guidance for Industry titled "Drug-induced Liver Injury: Premarketing Clinical Evaluation" issued by the FDA on July 2009:

FDA Guidance for Industry:

1. The drug causes hepatocellular injury, generally shown by a higher incidence of 3-fold or greater elevations above the ULN of ALT or AST than the (nonhepatotoxic) control drug or placebo.
2. Among subjects showing such AT elevations, often with AT levels much greater than $3 \times$ ULN, 1 or more also show elevation of serum TBL to $> 2 \times$ ULN, without initial findings of cholestasis (elevated serum ALP).
3. No other reason can be found to explain the combination of increased AT and TBL, such as viral hepatitis A, B or C; preexisting or acute liver disease; or another drug capable of causing the observed injury.

References

Temple R. Hy's Law: Predicting Serious Hepatotoxicity. *Pharmacoepidemiol Drug Saf.* 2006;15(4):241-3.

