7.3.6 Events of Clinical Interest Requiring Immediate Reporting (Cohort 9 only)

For cohort 9, selected non-serious and SAEs are also known as Events of Clinical Interest (ECI) and must be collected via the SAE worksheet or an applicable form (**Unique to Japan**) and reported to the sponsor within 24 hours of awareness as described in [Section 12.4.5 Reporting Procedures for Serious Adverse Events].

ECIs for this study include:

1. An overdose of sponsor's product, as defined in [Section 6.9 Treatment of Overdose], that is not associated with clinical symptoms or abnormal laboratory results.
2. An elevated AST or ALT laboratory value that is $\geq 3 \times \text{ULN}$ and an elevated TBL laboratory value that is $\geq 2 \times \text{ULN}$ and, at the same time, an alkaline phosphatase laboratory value that is $< 2 \times \text{ULN}$, as determined by way of protocol-specified laboratory testing or unscheduled laboratory testing.

Note: These criteria are based upon available regulatory guidance documents. The purpose of the criteria are to specify a threshold of abnormal hepatic tests that may require an additional evaluation for an underlying etiology. The study site guidance for assessment and follow up of these criteria can be made available. It may also be appropriate to conduct additional evaluation for an underlying etiology in the setting of abnormalities of liver blood tests including AST, ALT, bilirubin and alkaline phosphatase that do not meet the criteria noted above. In these cases, the decision to

proceed with additional evaluation will be made through consultation between the study investigators and the sponsor Medical Expert. However, abnormalities of liver blood tests that do not meet the criteria noted above are not ECIs for this study.

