12.4.1.2 Potential Cases of Drug-induced Liver Injury

Refer to [Appendix 12.5 Liver Safety Monitoring and Assessment] for detailed instructions on drug-induced liver injury. Abnormal values in AST and/or ALT concurrent or with abnormal elevations in TBL that meet the criteria outlined in [Appendix 12.5 Liver Safety Monitoring and Assessment], in the absence of other causes of liver injury, are considered potential cases of drug-induced liver injury (potential Hy's Law cases) and are always to be considered important medical events and reported per [Section 12.4.5 Reporting Procedures for Serious Adverse Events].

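### Appendix 12.5 makes SAE reporting optional for a potential Hy's Law case that Section 12.4.1.2 says must always be reported

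*Protocol*

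**What the plan says.** Protocol Section 12.4.1.2 covers potential drug-induced liver injury. It takes raised AST or ALT together with raised total bilirubin (TBL) "that meet the criteria outlined in [Appendix 12.5 Liver Safety Monitoring and Assessment], in the absence of other causes of liver injury", calls these potential Hy's Law cases, and says they "are always to be considered important medical events and reported per" Section 12.4.5. That section requires a completed SAE worksheet "to the sponsor by fax or email immediately (within 24 hours of awareness"). For the detail, 12.4.1.2 sends the site to Appendix 12.5.

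Appendix 12.5, Table 13, classes ALT or AST > 3 x ULN together with TBL > 2 x ULN as severe. It then widens the class: "the subject should be considered to have severe hepatic abnormalities for any of the following", with a list that includes ALT or AST > 8 x ULN alone. Under Follow-up Procedures it says that severe abnormalities "in the absence of another etiology may be considered an important medical event and may be reported as an SAE". The next sentence adds: "The sponsor should be contacted and informed of all subjects for whom severe hepatic liver function abnormalities possibly attributable to investigational product are observed". That sentence gives no deadline and names no form.

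For cohort 9 only, Section 7.3.6 makes AST or ALT >= 3 x ULN with TBL >= 2 x ULN and alkaline phosphatase (ALP) < 2 x ULN an ECI. Whether serious or not, an ECI "must be collected via the SAE worksheet or an applicable form" and reaches the sponsor within 24 hours.

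SAP Section 5.4 counts an adverse event as serious if the investigator flagged it, if the seriousness field is missing, or if the sponsor upgraded it. SAP Section 6.5.2.1 separately counts the combined ALT/AST and bilirubin pattern from laboratory values.

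**The concern.** One clinical picture is governed by two reporting instructions, one mandatory and one discretionary. The discretionary one sits in the appendix that a site is most likely to open when an abnormal liver result arrives, and the mandatory section itself points there. A site could leave the event off the SAE worksheet and believe that it had complied.

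What is at stake is timing and completeness. Under Section 12.4.5 the sponsor's assessment for expedited reporting starts from the SAE report, so a late or absent worksheet delays that assessment. In the analysis, the laboratory table could show a subject with the Hy's Law pattern while the serious TEAE tables show no matching event.

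**Working it through.** No arithmetic applies. The plan states no figure on this point and the documents report no case count. The check sets the provisions side by side for one event: ALT or AST > 3 x ULN with TBL > 2 x ULN, no other cause found.

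| Provision | Cohorts | Does it cover this event? | What the site must do | Deadline |
|---|---|---|---|---|
| Protocol 12.4.1.2 with 12.4.5 | All | Yes, by reference to the 12.5 criteria and only without another cause | Always report as an SAE | 24 hours |
| Protocol 12.5, Follow-up Procedures, reporting sentence | All | Yes, as severe under Table 13 and only without another etiology | May report as an SAE | None |
| Protocol 12.5, next sentence | All | Yes, if possibly attributable to study drug | Should inform the sponsor | None |
| Protocol 7.3.6 (ECI) | 9 only | Yes, if ALP < 2 x ULN | Report, serious or not | 24 hours |

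1. **Same event.** Section 12.4.1.2 borrows its criteria from Appendix 12.5, and Table 13 contains the combined elevation. The two sets overlap by construction.

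2. **Same condition.** Both rules apply only where no other cause explains the finding, so the condition does not separate them.

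3. **Different obligation.** The first row says always and the second says may. Both cannot govern one event.

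4. **Extent of the conflict.** The severe class in 12.5 is wider than Hy's Law. Section 12.4.1.2 concerns aminotransferase elevation combined with bilirubin elevation, so discretion over, say, ALT > 8 x ULN alone contradicts nothing there. The conflict is confined to the combined elevation.

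5. **What else would catch the case.**
   - Section 12.4.1.1 asks for clinically significant abnormal results unrelated to the underlying disease to be reported as adverse events. An AE record should therefore exist in every cohort.
   - Appendix 12.5 asks site staff to complete the liver abnormality CRF (LA-CRF) for confirmed moderate and severe abnormalities.
   - Section 12.4.2 lets either the investigator or the sponsor judge an event serious, and SAP 5.4 admits sponsor upgrades. An upgrade needs a recorded AE and does not replace the site's 24-hour report.
   - Appendix 12.5 mentions central-laboratory alerts, but only for studies that use a central laboratory. Here Section 7.2.2 and Appendix 12.7 send samples to local laboratories. Section 10.1 has a vendor enter the reports and transfer data at set intervals, which is not a 24-hour alert.
   - SAP 6.5.2.1 counts the pattern from laboratory values, including unscheduled visits, whatever the SAE status.

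6. **Who is most exposed.** Subjects without the ECI route. The synopsis plans about 320 subjects in 8 cohorts of about 40. Cohort 6 was reallocated and cohort 9 has the ECI route, which leaves cohorts 1 to 5, 7 and 8: 7 x 40 = about 280 planned. In cohort 9 a gap remains only where ALP is at or above 2 x ULN, or where the event is reported as a non-serious ECI and so does not enter the SAE tables.

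**The case against.** The strongest reply is that the texts can be read together. Appendix 12.5 describes itself as monitoring guidance and uses its permissive wording once for a broad class. Section 12.4.1.2 sets a specific rule for a subset and sits in the appendix that owns SAE definitions and reporting. The specific rule then governs, and a site sent from 12.4.1.2 to 12.5 has already met the mandatory wording.

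This reading is reasonable and probably what the sponsor intends, but it does not remove the conflict. The cross-reference runs from the mandatory rule to the permissive one, 12.5 carries no exception for the combined case, and a site may open 12.5 directly.

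The reply is right about the consequences. A reader might infer that a true case would vanish from the trial's safety record. The documents do not support that: the LA-CRF, the AE record, the sponsor notice and the laboratory table all remain, and an upgrade can restore the case to the SAE tables.

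A reader might also try to size the problem by comparing confidence limits for one case against none among about 320 subjects. That does not hold either. The SAP plans no confidence limits for SAE incidence, the laboratory table would still count the case, and 320 includes cohort 9, which has its own route.

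Finally, a reader might want the cohort 9 ECI definition aligned with Appendix 12.5. An ECI is a separate category that expressly admits non-serious events, and the protocol says its thresholds rest on regulatory guidance. The difference is not shown to be an error.

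**Conclusion.** The inconsistency is real and should be fixed. For ALT or AST > 3 x ULN with TBL > 2 x ULN and no other cause, the protocol both requires and merely permits SAE reporting. It is a drafting contradiction, not a design choice, and it touches neither the primary endpoint nor any stopping or decision rule.

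The realistic harm is an expedited report that is late or missed, mainly in cohorts 1 to 8, and serious TEAE tables that may not match the laboratory table. This assumes that a site follows the literal wording of Appendix 12.5. How often that has happened, or whether any qualifying case has occurred, cannot be told from the documents.

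**What to change.** - **Protocol Appendix 12.5, Follow-up Procedures.** State that concurrent ALT or AST > 3 x ULN and TBL > 2 x ULN without another cause is reported under 12.4.1.2 and 12.4.5 in all cohorts. Leave the permissive wording for the other severe categories.
- **Site memo.** Tell sites now which instruction applies, ahead of the next amendment.
- **One listing.** Match subjects who meet the combined criterion in SAP 6.5.2.1 against the SAE database, with LA-CRF information on possible etiology beside each. The laboratory criterion does not exclude other causes, so a subject without an SAE is a prompt for review and not automatically a missed report.

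The cost is one sentence, one memo, one listing and possibly a few more SAE reports. No analysis or sample size changes.
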